# 3.2 Secondary Objectives

The secondary objectives of this study are:

- To compare the phosphorus lowering effect of tenapanor and sevelamer alone in patients with sP >4.5 mg/dL to patients treated with a combination of tenapanor and sevelamer.
- To evaluate the effect of tenapanor alone and in combination with sevelamer on the proportion of patients reaching serum phosphorus targets defined as ≤4.5 mg/dL.
- To evaluate the effect of the addition of tenapanor to patients taking sevelamer on the percentage reduction in the sevelamer dose.
- To evaluate the effect of tenapanor alone and in combination with sevelamer on intact fibroblast growth factor 23 (iFGF23).
- To evaluate the effect of tenapanor alone and in combination with sevelamer on the Kidney Disease Quality of Life (KDQoL) survey.
- To evaluate the effect of tenapanor alone and in combination with sevelamer on the Dialysis Symptom Index (DSI) survey (for English speakers only).
- To compare the long-term safety of tenapanor alone and in combination with sevelamer.

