# 4.1.2 **Duration of Study**

The expected duration of each patient's participation in the study will be up to 18 months.

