#### 7.2.7 Adverse Events

The Investigator is responsible for ensuring that all staff involved in the study are familiar with the content of this section.

An AE is defined as any untoward medical occurrence in a patient administered a pharmaceutical product during the course of a clinical investigation. An AE can therefore be any unfavorable and unintended sign, symptom, or disease temporally associated with the use of an investigational product, whether or not thought to be related to the investigational product.

Patients will be monitored throughout the study for AEs, from the enrollment visit through the end of treatment (Visit 13). All AEs spontaneously reported by the patient or reported in response to the open question from the study personnel: "Have you had any health problems since the previous visit?", or revealed by observation will be collected and recorded in the eCRF. When collecting AEs, the recording of diagnoses is preferred (when possible) to recording a list of signs and symptoms. In instances of well-recognized symptoms, they can be recorded as the commonly used diagnosis (e.g., fever, runny nose, and cough can be recorded as "flu"). However, if a diagnosis is known, but there are other signs or symptoms that are not generally part of the diagnosis, the diagnosis and each sign or symptom should be recorded separately.

Adverse events that are identified at the last assessment Visit 13 (EOT) as specified in the protocol must be recorded on the AE eCRF with the status of the AE noted, and the AE must be followed until AE is resolved or stable. All events that are ongoing at this time will be recorded as ongoing on the eCRF. The procedures specified in Section 7.2.7.8 are to be followed for reporting SAEs.

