#### **Safety Analysis Set:**

All patients who receive at least one dose of study drug (tenapanor or sevelamer) in the study. The safety analysis set will be used for the analysis of safety variables.

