#### 9.4 Statistical Methods

### 9.4.1 General Approach

Unless specified otherwise, descriptive statistics including the number of observations, mean, standard deviation, median, minimum, and maximum will be presented for continuous variables. Frequency and percentage of patients will be presented for categorical variables.

Protocol No.: TEN-02-401

Edition No.: 1

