#### 9.4.4 Procedures for Handling Missing Serum Phosphorus Data

Descriptive summaries of efficacy and safety measures will be based on observed data. No imputation of missing data will be implemented.

Handling of missing data for each inferential analysis will be detailed in the SAP.

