### 9.4.7 Safety Analyses

Safety analyses include summaries for adverse events, clinical laboratory tests, vital signs, body weights, 12-lead ECGs, and physical examinations. These summaries will be provided for the Safety Analysis Set and each TEN-02-301 treatment arm (tenapanor or sevelamer).

Adverse events will be coded using the Medical Dictionary for Regulatory Activities (MedDRA). Summary tables and listings will be provided by system organ class and preferred term for treatment-emergent adverse events (TEAEs). Actual values and change from baseline values for clinical laboratory tests, vital signs, body weights, and ECGs will be descriptively summarized by visit. The number and percentage of patients in each physical examination category will be presented by visit.

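### AE percentages over all dosed patients can distort the long-term safety comparison if early withdrawal differs between the arms; time-based summaries should stand beside them

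*Combined protocol and SAP*

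**What the plan says.** A comparison of long-term safety is a secondary objective (Section 3.2): "To compare the long-term safety of tenapanor alone and in combination with sevelamer".

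The planned output is descriptive. Section 9.4.7 states "Summary tables and listings will be provided by system organ class and preferred term for treatment-emergent adverse events (TEAEs"), and then "These summaries will be provided for the Safety Analysis Set and each TEN-02-301 treatment arm (tenapanor or sevelamer"). No AE statistic is named there. The general rule in Section 9.4.1 is "Frequency and percentage of patients will be presented for categorical variables".

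The denominator is the Safety Analysis Set (Section 9.3): "All patients who receive at least one dose of study drug (tenapanor or sevelamer) in the study". Membership does not depend on time on study.

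Follow-up varies. Section 4.1.2 says "The expected duration of each patient's participation in the study will be up to 18 months", and Section 5.3 lets patients stop at any time. Section 7.2.7 sets the collection window: "Patients will be monitored throughout the study for AEs, from the enrollment visit through the end of treatment (Visit 13"). Under Sections 5.3 and 8.7 a withdrawing patient has the Visit 13 procedures at that point. Events already present are followed further, but no collection of new ones is described.

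Section 9.4.4 adds: "Descriptive summaries of efficacy and safety measures will be based on observed data", with no imputation. The protocol nowhere mentions exposure duration, patient-years, time to first event or cumulative incidence. Section 9.1 refers to a separate SAP that governs where the two differ. The text of that SAP is not in the material reviewed.

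**The concern.** A percentage with all dosed patients in the denominator gives a patient seen for three weeks the same weight as one seen for 18 months. For an event that keeps occurring over the study, less observation means fewer events counted, whatever the true rate. If one arm is observed for less time, its percentage falls further below its true 18-month risk, and that arm can look safer for no other reason.

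The design gives some reason to expect unequal retention. Under Section 6.1.4 the arms are carried over from TEN-02-301 and not re-randomised. Tenapanor-arm patients enter having completed the parent study and continue at their existing dose (Section 6.1.3). Sevelamer-arm patients start tenapanor at entry (Section 4.1.1), a drug that Section 7.2.7.1 says alters stool form and frequency in some patients.

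At stake is the reading of the one objective that concerns long-term safety.

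**Working it through.** **Stated figures.** There is none to reproduce. Section 9.2 says that the sample size (150 to 200) has no statistical basis, and no dropout or AE rate is given. The only input from the documents is the horizon, T = 18 months = 1.5 years. All rates below are assumptions.

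**Model.** First-event hazard L and dropout hazard M are both constant per year, and dropout is independent of the event.

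- Crude percentage = L/(L+M) × [1 − exp(−(L+M)T)]
- Person-time to first event or dropout = [1 − exp(−(L+M)T)]/(L+M)
- First-event rate = crude percentage / person-time = L
- Conversion from an 18-month risk or dropout proportion p: hazard = −ln(1−p)/1.5

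**1. Same true risk in both arms.** Dropout of 10%, 20%, 30%, 40% and 50% by Month 18 corresponds to M = 0.070, 0.149, 0.238, 0.341 and 0.462 per year. Mean time on study is 16.1 months at 20% dropout and 14.1 months at 40%.

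| True 18-month risk | L per year | Crude %, dropout 20% vs 40% | Gap, 20% vs 20% | Gap, 20% vs 30% | Gap, 20% vs 40% | Gap, 10% vs 50% |
|---|---|---|---|---|---|---|
| 10% | 0.070 | 9.0 vs 7.9 | 0 | 0.5 | 1.1 | 2.2 |
| 20% | 0.149 | 18.0 vs 15.8 | 0 | 1.1 | 2.2 | 4.4 |
| 40% | 0.341 | 36.2 vs 32.0 | 0 | 2.0 | 4.2 | 8.4 |
| 60% | 0.611 | 54.7 vs 48.8 | 0 | 2.9 | 5.9 | 11.9 |

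Gaps are in percentage points. With equal dropout there is no gap, though both arms still understate the 18-month risk (18.0% against 20%).

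**2. Strongly unequal dropout.** Take M = 0.15 versus 0.60. Dropout by Month 18 is 1 − exp(−0.225) = 20% versus 1 − exp(−0.9) = 59%. With L = 0.5 in both arms:

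- 0.5/0.65 × [1 − exp(−0.975)] = 0.769 × 0.623 = 47.9%
- 0.5/1.10 × [1 − exp(−1.65)] = 0.455 × 0.808 = 36.7%

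The false gap is 11.2 points.

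**3. Reversal.** Raise L to 0.6 in the high-dropout arm, a true hazard 20% higher. Its crude figure is 0.6/1.2 × [1 − exp(−1.8)] = 0.5 × 0.835 = 41.7%, still below 47.9%. The arm with the higher hazard looks safer.

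**4. Events confined to month 1.** Crude percentages are then almost right. At a true risk of 20% and dropout of 20% versus 40% they are 19.9% versus 19.7%. At a true risk of 30% and M = 0.15 versus 0.60 they are 29.8% versus 29.3%.

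A single overall person-time rate now fails instead. With no true difference:

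- True risk 20%, dropout 20% versus 40%: 18.3 versus 20.8 per 100 patient-years.
- True risk 30%, M = 0.15 versus 0.60: 0.298/0.952 = 31 versus 0.293/0.704 = 42 per 100 patient-years.

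Splitting the second case at Month 3 removes most of this. Person-time to first event, dropout or Month 3 is 0.0697 + 0.1138 = 0.1835 years versus 0.0685 + 0.1056 = 0.1741 years, where the two terms are month 1 and months 2 to 3. The rates are 0.298/0.1835 = 163 versus 0.293/0.1741 = 168 per 100 patient-years. The false excess falls from about a third to about 3%.

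**The case against.** **Patients who leave because of an AE are already counted for it.** This stands. If sevelamer-arm patients leave because tenapanor upsets the gut, those events are in the numerator, and the crude comparison can point the right way. With common dropout of 0.15 per year and hazards of 0.5 versus 0.7, the percentages are 48% versus 59%. A reader might infer that the sevelamer arm will leave sooner and so look falsely safe. The documents do not support that: they give no dropout rate, and the reason for expecting more withdrawal is also a reason for expecting more recorded events. Neither arm can be named.

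**The size depends on the inputs.** This also stands. A reader who looked only at strongly unequal dropout might infer a large gap as the expected result. Milder dropout gives a few points, equal dropout gives none, and uncommon preferred terms move little in absolute terms.

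**A person-time rate is no cure by itself.** Correct: step 4 shows it creating a false difference for early events, which may include the GI terms of most interest.

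**The TEN-02-301 arm is not the contrast in the objective.** Correct. The objective concerns tenapanor alone and with sevelamer. Section 4.1.1 allows sevelamer to be added in the tenapanor arm, and in the sevelamer arm it provides for patients not taking sevelamer. Patient-years by arm alone would not serve the objective.

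**The SAP may already cover this.** Possible. Section 9.1 makes it govern, and the Section 9.4.1 default yields to anything more specific. A reader might infer that no time-based analysis was ever planned. All that is shown is a gap in the protocol text, although Section 9.4.7, unlike Section 9.4.3, does not defer its detail to the SAP.

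**Conclusion.** The point holds conditionally. As written, the protocol summarises AEs as percentages of all dosed patients by parent-study arm, over follow-up that varies and ends at withdrawal, and has no exposure or time-based summary. If early withdrawal differs between arms, those percentages understate the risk of accruing events more in the arm with shorter follow-up, and can distort or reverse the comparison.

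Step 1 spans a false gap of 0 (equal dropout) to 11.9 points (10% versus 50% dropout, true risk 60%), with about 1 to 6 points at 20% versus 40%. For events limited to the first month it is near 0. These figures assume constant hazards (except for the month-1 case), dropout independent of AEs, and rates that the documents do not give. Section 9.4.7 plans summaries and no between-arm safety test, so the risk is a misread table, not a wrong test result. This is an inexpensive improvement worth making, not a fault that invalidates the study.

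**What to change.** In Section 9.4.7, or in the SAP if it does not already say so, keep the percentages and add:

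1. Duration of exposure and patient-years by TEN-02-301 arm and by regimen (tenapanor alone, tenapanor with sevelamer), with each patient's time split when the regimen changes. Regimen follows serum phosphorus, so the regimen figures are descriptive.
2. As the main time-based summary, cumulative incidence of first event by arm for any TEAE, SAEs, the main GI terms and discontinuation due to AE. State how withdrawal and death are handled.
3. First-event rates per 100 patient-years with 95% CIs, split by period (for example, to Month 3 and after). Do not report one overall rate alone, because it can create a false difference for early events.

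The cost is wording plus a few more tables and figures, with no new visits or procedures. One check comes first. The protocol lists severity, action taken, outcome and reason for withdrawal as recorded items, but does not state that AE onset and last-dose dates are captured. Confirm that the eCRF holds them, along with the dates of sevelamer starts and stops.

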#### 10 ACCESS TO SOURCE DATA/DOCUMENTS

The Investigator will provide direct access to source data and documents for the Sponsor or its designee conducting study-related monitoring and/or audits, IRB/ Independent Ethics Committee (IEC) review, and regulatory review. The purpose of an audit or inspection is to systematically and independently examine all study-related activities and documents, to determine whether these activities were conducted, and data were recorded, analyzed, and accurately reported according to the protocol, GCP (Good Clinical Practice), guidelines of the International Conference on Harmonization (ICH), and any applicable regulatory requirements. The Investigator will contact the Sponsor immediately if contacted by a regulatory agency about an inspection at any clinical site.

The Investigator must inform the study patient that his/her study-related records may be reviewed by the above individuals without violating the patient's privacy of personal health information in compliance with regulations of the Health Insurance Portability and Accountability Act of 1996 (HIPAA).

Protocol No.: TEN-02-401

Edition No.: 1

Attention is drawn to the regulations promulgated by the FDA under the Freedom of Information Act providing, in part, that information furnished to clinical Investigators and IRBs will be kept confidential by the FDA only if maintained in confidence by the Investigator and IRB. By signing this protocol, the Investigator affirms to the Sponsor that the Investigator will maintain, in confidence, information furnished to him or her by the Sponsor and will divulge such information to the IRB under an appropriate understanding of confidentiality with such board.

### 11 OUALITY CONTROL AND QUALITY ASSURANCE

The Sponsor or its designee will implement and maintain quality control and quality assurance procedures with written SOPs to ensure the study is conducted and data are generated, documented, and reported in compliance with the protocol, GCP, and applicable regulatory requirements.

#### 11.1 Conduct of Study

This study will be conducted in accordance with the provisions of the Declaration of Helsinki and all revisions thereof, and in accordance with the FDA Code of Federal Regulations (21 CFR Parts 11, 50, 54, 56, 312) and the International Conference on Harmonization (ICH) Guidelines on good clinical practice (ICH E6 R2). Specifically, this study is based on adequately performed laboratory and animal experimentation; the study will be conducted under a protocol reviewed by an IRB or IEC; the study will be conducted by scientifically and medically qualified persons; the benefits of the study are in proportion to the risks; the rights and welfare of the patients will be respected; the physicians conducting the study do not find the hazards to outweigh the potential benefits; and each patient will give his or her written, informed consent before any protocol-driven tests or evaluations are performed.

The Investigator may not deviate from the protocol without a formal protocol amendment having been established and approved by an appropriate IRB, except when necessary to eliminate immediate hazards to the patient. Any deviation may result in the patient having to be withdrawn from the study, and may render that patient non-evaluable.

#### 11.2 Protocol Amendments

Only the Sponsor may modify the protocol. All amendments that have an impact on patient risk or the study objectives, or require revision of the ICF, must receive approval from the IRB prior to their implementation. Should the protocol changes be significant i.e., where there are changes in the existing protocol that significantly affect safety of patients, scope of

Protocol No.: TEN-02-401

Edition No.: 1

the investigation, or scientific quality of the study, the Sponsor must submit the protocol to the FDA prior to the protocol amendment being implemented.

#### 11.3 Monitoring of Study

The Investigator will permit the site monitor to review study data as frequently as is deemed necessary to ensure data are being recorded in an adequate manner and protocol adherence is satisfactory.

The Investigator will provide access to the source documents or provide certified copies of the medical records for the monitor to verify eCRF entries. The Investigator is expected to cooperate with the Sponsor/designee in ensuring the study adheres to GCP requirements.

#### 11.4 Ethics

### 11.5 Institutional Review Board/Independent Ethics Committee Approval

#### 11.5.1 Ethics Review Prior to Study

The Investigator will ensure that the protocol and consent form are reviewed and approved by the appropriate IRB prior to the start of any study procedures. The IRB will be appropriately constituted and perform its functions in accordance with FDA regulations, ICH GCP guidelines, and local requirements as applicable.

#### 11.5.2 Ethics Review of other Documents

In addition, the IRB will approve all protocol amendments (except for Sponsor-approved logistical or administrative changes), written informed consent documents and document updates, patient recruitment procedures, written information to be provided to the patients, available safety information, information about payment and compensation available to patients, the Investigator's curriculum vitae and/or other evidence of qualifications, and any other documents requested by the IRB and regulatory authority as applicable.

#### 11.6 Written Informed Consent

The nature and purpose of the study will be fully explained to each patient (or the patient's legally responsible guardian). The patients must be given ample time and opportunity to inquire about details of the trial, to have questions answered to their satisfaction, and to decide whether to participate. Written informed consent must be obtained from each patient (or guardian) prior to any study procedures being performed.

Protocol No.: TEN-02-401

Edition No.: 1

### 12 DATA HANDLING AND RECORD KEEPING

# 12.1 Data Reporting and Case Report Forms

### 12.1.1 Case Report Forms

The Investigator will be provided with eCRFs, and will ensure all data from patient visits are promptly entered into the eCRFs in accordance with the specific instructions given. The Investigator must sign the eCRFs to verify the integrity of the data recorded.

## 12.1.2 Laboratory Data

A list of the normal ranges for all laboratory tests to be undertaken forms part of the documentation to be distributed to all sites. The Investigator must maintain source documents such as laboratory reports and complete history and physical examination reports.

#### 12.1.3 Retention of Source Documents

The Investigator must maintain source documents such as laboratory reports, x-rays, ECGs, consultation reports, and complete history and physical examination reports.

#### 12.2 Retention of Essential Documents

Essential documents should be maintained for at least 11 years based upon the Sponsor's requirements and may be required to be maintained longer based upon applicable regional regulatory requirements. The Investigator/institution should take measures to prevent accidental or premature destruction of these documents. Should the Investigator/institution not be able to maintain the records for this period of time, or there is a change in site location, the Investigator/institution must inform the Sponsor in writing, via certified mail, at least 90 days prior to the destruction of any study documents, so that the Sponsor has the option, at the Sponsor's expense, to have the records stored for a longer period of time. It is the responsibility of Sponsor to inform the Investigator/institution as to when these documents no longer need to be retained.

Protocol No.: TEN-02-401

Edition No.: 1

